3.7 Coding dictionaries

Adverse events (AEs) will be coded using the Medical Dictionary for Regulatory Activities (MedDRA), Version 20.0.

Medications will be coded using the most recent World Health Organization Drug Reference List (WHODD) Version (MAR/2018).

4 STATISTICAL/ANALYTICAL ISSUES

4.1 Adjustments for covariates

Conventional multiple regression analysis and propensity score analysis will include (but are not limited to) the following Baseline characteristics in the initial run of the model.

Characteristics that are continuous will remain as such. Categorical variables will use the values in parentheses:

- Age
- Gender (Male, Female)
- Race (American Indian/Alaskan native, Asian, Black, Native Hawaiian/Pacific Islander, White, Other/Mixed)
- Smoking status (Never, Current, Former)
- Other biologic treatment use in the year prior to Baseline (Yes, No)
- Immunosuppressant use in the year prior to Baseline (Yes, No)
- Corticosteroid use in the year prior to Baseline (Yes, No)
- Disease extent (Ileum, Colon, Illeocolon, Upper GI, Ileum + upper GI, Colon + upper GI, Illeocolon + upper GI, Other)
- Diagnosed with fistulas (Yes, No)
- Duration of disease
- Physician assessment of disease severity (Remission, Mild-moderate, Moderate-severe, Severe)
- Number of Crohn's related hospitalizations in the year prior to Baseline
- Number of surgical resections in the year prior to Baseline
- Calendar year of enrollment

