6.4.1.3.1 Propensity score variables

Propensity scores will be calculated for each patient using all collected, potential confounding variables. These variables include (but are not limited to) the following Baseline characteristics:

- Age
- Gender
- Race

- Smoking status
- Other biologic treatment use in the year prior to Baseline
- Immunosuppressant use in the year prior to Baseline
- Corticosteroid use in the year prior to Baseline
- Disease location
- Diagnosed with fistulas
- Duration of disease
- Investigator assessment of disease severity
- Number of Crohn's related hospitalizations in the year prior to Baseline
- Number of surgical resections in the year prior to Baseline
- Disease extent

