2.3.1 Patient Inclusion/Exclusion Criteria

Patients who meet all of the following criteria will be eligible for inclusion into the SECURE Registry:

- Patient (or his/her legally acceptable representative) is able to provide written informed consent to permit collection of data.
- Patient must be 18 years of age or older.
- Patient must have medically documented CD.
- The decision to prescribe Cimzia or other medications has been made by the physician independently of the decision to include the patient in the study.
- Patients participating in randomized, blinded clinical trials for CD or other conditions are not eligible for inclusion into the SECURE registry. Involvement in other registries, where patients follow routine clinical practice, is permitted, however.
- The rules for handling erroneous patient entries are laid out in a separate Analysis Data Reviewers Guide.

Cimzia-treated patients

For a patient to qualify as being treated with Cimzia, they must meet one of the following criteria:

- Patient is receiving treatment with Cimzia for the first time. Patient must receive Cimzia treatment within 2 months of enrollment into the registry.
- Patient is currently receiving treatment with Cimzia for ≤ 12 months. Patients must also receive a Cimzia dose within 2 months following enrollment into the registry.

Comparator patients

Patients enrolled in the comparator group are eligible to participate in the registry if one of the following criteria is fulfilled:

- Patient is switching CD treatments or beginning CD treatment for the first time. Previous Cimzia treatment is prohibited in the comparator group. Patient must receive new CD treatment within 2 months of enrollment into the registry.

- Patient is currently receiving other biologic treatment (excluding Cimzia) for ≤ 12 months. Patient must receive other biologic treatment within 2 months following enrollment into the registry.
- Patient is currently receiving immunosuppressant therapy for ≤ 12 months. Patient must receive immunosuppressant therapy within 2 months following enrollment into the registry.
- Patient is currently receiving systemic steroid therapy for ≤ 12 months. Patient must receive systemic steroid therapy within 2 months following enrollment into the registry.

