3.3 Definition of Baseline values

In general Baseline values will be determined from the study entry visit (enrollment visit, screening visit, and Baseline visit used interchangeably).

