8.1.2.1 Propensity score estimation

The propensity score represents the probability that a specific patient receives Cimzia conditional on a set of known baseline confounding factors (4). A logistic regression model, with treatment cohort as the dependent variable, will be employed to estimate the conditional distribution of the treatment given the covariates. The predictors in this model are pre-treatment variables believed to be related to the study outcome of interest and are listed in Section 8.1.2 These variables were

selected a priori using a directed acyclic graph (DAG). This approach has the advantage of improving the statistical efficiency of a model. It also minimizes the introduction of bias which may result from more traditional confounder identification and adjustment approaches (5).

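### For comparators who enroll already on treatment, the drug-history flags in the propensity score record the comparator drug itself, so the flags do not measure the same thing in the two cohorts

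*SAP*

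**What the plan says.** SAP 4.1 lists the covariates for the propensity score and the conventional regression. Three of the fourteen are drug-history flags: "Other biologic treatment use in the year prior to Baseline (Yes, No"), "Immunosuppressant use in the year prior to Baseline (Yes, No") and "Corticosteroid use in the year prior to Baseline (Yes, No"). SAP 8.1.2 repeats them, and Protocol 6.4.1.3.1 has the same variables ("Other biologic treatment use in the year prior to Baseline"). Neither document excludes the drug that put the patient in the cohort.

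The anchor date is in SAP 3.3: "In general Baseline values will be determined from the study entry visit". SAP 8.1.2.1 describes the score's inputs thus: "The predictors in this model are pre-treatment variables believed to be related to the study outcome of interest".

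SAP 2.3.1 admits patients already on treatment to both cohorts. One comparator route reads "Patient is currently receiving other biologic treatment (excluding Cimzia) for" up to 12 months. Parallel routes cover immunosuppressants and systemic steroids. A Cimzia patient may likewise have been on Cimzia for up to 12 months.

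**The concern.** A drug-history covariate is meant to record what the patient had received before the treatment under study. Among comparators who enroll as prevalent users, the flag for their class is instead set by the treatment under study. Among Cimzia patients, the biologic flag can be set only by a different biologic. The same Yes therefore describes two kinds of patient: one who has used another biologic besides Cimzia, and one who may simply be continuing a first biologic.

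Matching can pair these two and report them as balanced. The standardized-bias check in SAP 8.1.2.4 is computed on the recorded flag, so it sees no difference. The residual adjustment in the same section acts only on covariates that fail that check. The conventional regression in SAP 8.1.5, offered as a robustness assessment, uses the same covariate vector and so carries the same error. What is at stake is how far the matched and adjusted comparisons control for treatment history.

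**Working it through.** **Step 1: trace each entry route through the look-back (SAP 2.3.1, 3.3, 4.1).**

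- Comparator already on a biologic, immunosuppressant or systemic steroid: the flag for that class is Yes with certainty. Such a patient cannot be No on all three flags.
- Comparator starting or switching at or after enrollment: the new drug lies outside the look-back, so the flag reflects earlier use.
- Cimzia patient already on Cimzia for m months: Cimzia sets no flag, no listed covariate records time on Cimzia, and only 12 − m months of the look-back precede Cimzia (12, 9, 6, 3, 0 for m = 0, 3, 6, 9, 12).

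This step needs no assumed numbers.

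**Step 2: illustrate the size for the biologic flag.** The plan has no figure to reproduce, and none of the next three inputs is in the documents:

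- v = share of comparators enrolled as prevalent users of a non-Cimzia biologic
- p₀ = true biologic use before the qualifying drug, comparators
- p_C = the same in Cimzia patients

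The model assumes that v is unrelated to true history, that the flag is correct for Cimzia patients, and that matching is exact on this flag alone.

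- Recorded Yes in comparators: r = v + (1 − v)p₀
- True prior use in matched comparators: q = p_C × p₀ / r
- Standardized difference, by the two-level formula in SAP 8.1.2.4: (p_C − q) / √(0.5[p_C(1 − p_C) + q(1 − q)])

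Worked case, p_C = 0.50, p₀ = 0.20, v = 0.40:

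- r = 0.40 + 0.60 × 0.20 = 0.52, of which 0.20/0.52 = 38% is true prior use.
- q = 0.50 × 0.20/0.52 = 0.192.
- Hidden difference after matching = (0.50 − 0.192)/√(0.5[0.25 + 0.155]) = 0.68.
- True difference before matching = (0.50 − 0.20)/√(0.5[0.25 + 0.16]) = 0.66.
- Recorded difference before matching = (0.50 − 0.52)/√(0.5[0.25 + 0.2496]) = −0.04, so the flag looks balanced from the outset.

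The same formulas at other inputs:

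| p_C | p₀ | v | r | q | True difference before matching | Hidden difference after matching |
|---|---|---|---|---|---|---|
| 0.50 | 0.50 | 0.10 | 0.550 | 0.455 | 0.00 | 0.09 |
| 0.50 | 0.30 | 0.10 | 0.370 | 0.405 | 0.42 | 0.19 |
| 0.70 | 0.40 | 0.10 | 0.460 | 0.609 | 0.63 | 0.19 |
| 0.50 | 0.50 | 0.25 | 0.625 | 0.400 | 0.00 | 0.20 |
| 0.50 | 0.50 | 0.50 | 0.750 | 0.333 | 0.00 | 0.34 |
| 0.50 | 0.20 | 0.40 | 0.520 | 0.192 | 0.66 | 0.68 |

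The recorded difference after matching is 0 in every row.

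**Step 3: the corrected anchor.** Ending the look-back at the start of the qualifying drug and excluding that drug is v = 0 in this model. Then r = p₀, q = p_C and the hidden difference is 0.

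**The case against.** **The SAP already separates incident from prevalent users.** SAP 4.5 and 8.1.5 stratify the primary acute-event analysis this way, and the incident stratum is largely free of the problem. This stands and limits the point. But the split is stated for acute events only, and the matching in SAP 8.1.2.3 is not done within strata. Table 8.1 adds an acute-rule analysis of malignancies, but nothing says the split applies to it. Within the prevalent stratum, every comparator has at least one flag set by the study drug.

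**By the SAP's own terms the flags are pre-treatment.** SAP 3.6 sets treatment start at informed consent, so a look-back from enrollment comes before it. This removes the charge that the SAP breaks its own rule. It does not make the flags comparable: SAP 8.1.5 itself defines prevalent users as already treated before enrollment.

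**The word other could mean other than the current drug.** SAP 2.3.1 and 3.6 use it for biologics other than Cimzia, and the immunosuppressant and steroid flags do not carry the word. If an exclusion is intended, it needs writing down.

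**The figures are driven by assumptions.** This stands. The 0.68 mostly returns the 0.66 assumed at the start. Disease duration, severity, fistulas, hospitalizations and resections are also in the score and may carry part of the same information. A reader might infer that the hidden difference always exceeds the 0.2 limit; at a 10% prevalent biologic share it does not.

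**The stakes are descriptive.** The SAP plans no formal hypothesis testing. However, SAP 8.1.2.2 uses the retained patients to estimate treatment effects, and hazard ratios and rate ratios with intervals will be reported and read.

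**Conclusion.** The mismatch is real and follows from the definitions in SAP 2.3.1, 3.3 and 4.1. It is confined to comparators who enroll as prevalent users and to the three drug-history flags. It does not affect flags for patients starting treatment at enrollment, or covariates such as age and sex, so the documents do not support a reading that the whole match is invalid.

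The size is unknown, because the prevalent share and true prior use in each cohort are not in the documents. The illustrations run from 0.09 to 0.68 against a limit of 0.2. With truly equal cohorts (50% each), matching on the flag creates an imbalance of about 0.20 once a quarter of comparators are prevalent biologic users.

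A reader might also infer that the bias runs against Cimzia. Within the model, matched comparators do have less true prior biologic use, since q is below p_C whenever v > 0 and p₀ < 1. The step to higher risk in the Cimzia cohort holds only if prior biologic use marks higher risk, which the documents do not establish.

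The main gap is malignancy, the primary outcome, together with the matching and the prevalent stratum for acute events. The plan should be changed here, but the evidence does not show that its results would be materially wrong.

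**What to change.** In SAP 4.1 and 8.1.2:

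- Define the three flags over the year before the start of the cohort-qualifying treatment, excluding that treatment. For patients starting at enrollment this equals the present definition.
- For comparators on more than one qualifying class at enrollment, use the earliest start among the qualifying drugs being taken then, and exclude all of them.
- Flag patients whose start date is wholly unknown. SAP 4.2 can impute it to the consent date, which makes a prevalent user look like a new starter. A start known only by year, when that is the consent year, is imputed in the same way and deserves the same mark.
- Match within incident/prevalent strata.
- Extend the incident/prevalent split in SAP 4.5 and 8.1.5 to malignancy.
- Keep the enrollment-anchored flags as a sensitivity analysis, and report the prevalent share by class so that the size can be judged.

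No new data are needed: Protocol 4.8.1 collects all past treatment for Crohn's disease. The cost is SAP wording and re-derivation of three flags. Some look-back windows will rest on partial historical dates, and matching within strata may lose some pairs. Severity, hospitalizations and resections would still be measured from enrollment.

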4.2 Handling of dropouts or missing data

For HBI scores, all missing values will remain as missing. No attempt will be made to impute missing values. Only observed values will be used in data analyses and presentations.

For both the physician and patient reported HBI, the use of eCRFs will allow the total score to be computed and therefore not require the recording of the total HBI score. However, for the physician reported HBI, if any of the first 4 parameters are missing, then the total HBI score will be set to missing. For the patient reported HBI, if any of the first 3 parameters are missing, then the total HBI score will be set to missing.

Missing safety data, in general, will not be imputed. However, if relationship to CD treatment is missing for an AE, the event will be categorized as having a reasonable possibility of being caused by the treatment for the summary of AEs by relationship.

Concomitant medications will be imputed as described below in accordance with the GSS global conventions document version 1.1.

The following rules are applied to impute partial start and stop dates for medications.

Imputation of Partial Start Dates

- If only the month and year are specified and the month and year of informed consent is not the same as the month and year of the start date, then use the 1st of the month.
- If only the month and year are specified and the month and year of informed consent is the same as the month and year of the start date, then use the date of informed consent.
- If only the year is specified, and the year of informed consent is not the same as the year of the start date, then use January 1 of the year of the start date.
- If only the year is specified, and the year of informed consent is the same as the year of the start date, then use the date of informed consent.
- If the start date is completely unknown, and the stop date is unknown or not prior to the date of informed consent, then use the date of informed consent.

Imputation of Partial Stop Dates

- If only the month and year are specified, then use the last day of the month.
- If only the year is specified, then use December 31 of that year.
- If the stop date is completely unknown, do not impute the stop date.

In the event of ambiguity or incomplete data which makes it impossible to determine whether a medication was concomitant or not, the medication will be considered as concomitant.

4.3 Interim analyses and data monitoring

Data captured for the study will be analyzed periodically, and at the end of the study. Supplemental data analyses may be performed throughout the study in addition to the periodic and final analyses.

Quarterly progress reports will be sent to the FDA during the patient recruitment period. Further, more detailed informal interim analyses will be conducted yearly during the follow-up portion of the study in order to provide the steering committee and FDA regular updates.

Supplemental data analyses may be performed throughout the study in addition to the periodic and final analyses.

4.4 Multiple comparisons/multiplicity

No adjustments for multiple comparisons will be made as all statistical testing will be considered descriptive in nature.

4.5 Examination of subgroups

The primary analysis for acute events will be stratified on incidence/prevalence use (yes/no).

The impact of data from the high accruing study site #849 on key outcomes will be assessed (Clinical site closed due to significant noncompliance; reported to FDA's Division of Scientific Investigations in letter dated 29 April 2020).

If sufficient power exists, further stratification based on duration of prevalent use (e.g., 1-5 months, 6+ months, etc.) may be performed. This is described in more detail in Section [8.1.5](#).

5 STUDY POPULATION CHARACTERISTICS

5.1 Subject disposition

The number and percentage of patients who enrolled and the number and percentage of patients who completed the study will be presented, together with the number and percentage of patients who withdrew from the study prematurely and a breakdown of the corresponding reasons for discontinuation will be produced by enrollment cohort and actual treatment at Baseline.

A Cox proportional hazards model utilizing Kaplan-Meier methods for time to discontinuation by year 1, year 2, ..., year 8, will be performed by enrollment cohort and actual treatment at Baseline. Discontinuation status, discontinuation time (median, 25th and 75th quartiles and corresponding two-sided 95% confidence intervals), and a hazard ratio and exploratory p-value from a log-rank test at $\alpha=0.05$ overall significance level will be included for the analysis of each year.

A Cox proportional hazards model utilizing Kaplan-Meier methods for time to discontinuation by year 1, year 2, ..., year 8, will be performed by enrollment cohort and actual treatment at Baseline. Discontinuation status, discontinuation time (median, 25th and 75th quartiles and corresponding two-sided 95% confidence intervals), and a hazard ratio and exploratory p-value from a log-rank test at $\alpha=0.05$ overall significance level will be included for the analysis of each year.

A summary of expected and actual patient retention by enrollment cohort and actual treatment at Baseline will include total patient-years and the number of patients followed for at least 1 year, at least 2 years, ..., at least 8 years.

Time to discontinuation will be analyzed using two different censoring rules (A and B).

According to censoring rule A, the time for patients in the Cimzia cohort will be censored when they switch to Comparator treatment and the time for patients in the Comparator cohort will be censored when they switch to Cimzia treatment. According to censoring rules B, time for all patients will be censored when they switch from one biologic treatment to another biologic treatment.

A table summarizing the number and percentage of patients enrolled at each site by enrollment cohort will be presented.

5.2 Protocol deviations

A table summarizing the number and percentage of patients who had any important protocol deviations by enrollment cohort will be presented. A listing of all patients who had any important protocol deviations during the study will be provided. See Section 3.4 for important protocol deviation definitions.

6 DEMOGRAPHICS AND OTHER BASELINE CHARACTERISTICS

6.1 Demographics and other baseline characteristics

Demographic and baseline characteristics include age, gender, race, ethnicity, height, weight, socioeconomic status (employment status and annual income) and smoking status and will be summarized by enrollment cohort and actual treatment at Baseline. Age will be calculated based on the date of informed consent. If data are available, the demographic analysis will include a summary for physical examination findings and vital sign values.

Listings of demographics and baseline characteristics will be provided.

6.2 Medical history

The number and percentage of patients who had medical history conditions of interest will be summarized by enrollment cohort and actual treatment at Baseline. Family medical history for anyone in each patient's immediate family (defined as the patient's biological parents and siblings) who had medical history conditions of interest will be summarized by enrollment cohort and actual treatment at Baseline. In addition, the number and percentage of patients with CD history will be summarized by enrollment cohort and actual treatment at Baseline.

Listings of medical history, family medical history, CD history, and CD medication history will be provided.

6.3 Concomitant medications

Medications received concomitantly with Cimzia or any non-Cimzia CD medication, categorized at each analysis by drug class, and by the most recently available version of the WHO Drug preferred term, will be summarized for the Enrolled Set and using actual treatment based on the acute event rules. The number and percentage of patients using each medication will be displayed. The number and percentage of patients for each level of the covariates listed in Section 4.1 will be presented. Concomitant medications will be defined as medications that started on or after the date of enrollment.

7 MEASUREMENTS OF TREATMENT COMPLIANCE

Not applicable.

8 PRIMARY ANALYSES

The primary outcome of this observational study is malignancy (malignant tumors and malignant or unspecified tumors). However, in addition, the following list of AEs of interest will be

summarized using cumulative incidence (proportion) and incidence rate (events per 100 patient-years). These AEs are described in section 8.2.3 and defined in detail in the AE of interest – Cimzia Program 2018-01-05 document.

- Serious infections
- Opportunistic infections
- Serious cardiovascular events (also called major adverse cardiac events, or MACE)
- Congestive heart failure
- Demyelinating-like disorders
- Aplastic anemia, pancytopenia, thrombocytopenia, neutropenia and leucopenia
- Serious bleeding events
- Lupus and lupus-like illness
- Serious skin reactions

Although not officially AEs of interest, the following events will also be summarized as described in the AEs of Interest – Cimzia Program 2018-01-05 guidance document.

- Hepatic Events
- Hypersensitivity reactions and anaphylactic reactions

Separate from the AEs of interest document, malignant lymphomas, non-melanoma skin cancer, and autoimmune disorders will also be summarized.

